2. OBJECTIVES

Aim 1: To evaluate the effect of treatment with lorcaserin hydrochloride compared to placebo on the change in baseline biomarkers of adiposity and metabolic dysregulation, dysglycemia and its complications, and CV risk (atherosclerosis, ischemia, inflammation, thrombosis, hemodynamic stress and lipid dysregulation) over the data acquisition period.

We hypothesize that lorcaserin hydrochloride will improve circulating concentrations of biomarkers of these conditions/processes over time compared to placebo.

Aim 2: To evaluate the prognostic performance of established and novel biomarkers of adiposity and metabolic dysregulation, dysglycemia and its complications, and CV risk (atherosclerosis, ischemia, inflammation, thrombosis, hemodynamic stress and lipid dysregulation) individually and in combination (multimarker approach).

We hypothesize that baseline biomarkers can identify subgroups of overweight or obese subjects at increased risk of major adverse cardiovascular outcomes and/or the development of diabetes. Furthermore, we hypothesize that a multi-marker approach can improve discrimination, accuracy, and net reclassification improvement of models predicting the development or progression of these disorders.

Aim 3: To evaluate whether obese subjects identified at higher risk on the basis of biomarkers experience greater absolute and/or relative risk reduction in major adverse cardiovascular outcomes and/or the development of diabetes with lorcaserin HCl versus placebo.

We hypothesize that subjects with the highest risk biomarker profiles will observe greatest benefit from treatment with lorcaserin hydrochloride.

Aim 4: To evaluate the prognostic significance of the change in the levels of established and novel biomarkers of adiposity, inflammation, hemodynamic stress, myocardial ischemia/necrosis and metabolism between baseline and 6 month, and whether changes in biomarker concentration identify subjects with greater benefit with lorcaserin HCl versus placebo.

We hypothesize that the change in levels of biomarkers between baseline and 6 months can identify subgroups of overweight or obese subjects at increased risk of major adverse cardiovascular outcomes and/or the development of diabetes, who are likely to derive greater benefit from treatment with lorcaserin HCl.

3 BIOLOGIC RESEARCH PLAN AND PROCEDURES

This appendix to the Clinical Study Protocol has been subjected to peer review according to Eisai standard procedures. Collection of the biomarker samples will be bound by the sample

principles and processes outlined in the main study protocol. Sample collection for biomarker analysis is required as per the study protocol unless the collection and use of the samples is prohibited by specific country laws.

3.1 Selection of biologic research population

3.1.1 Study selection record

All subjects will be asked to participate in this biologic research (except where prohibited by local regulations). Participation is voluntary and if a subject declines to participate there will be no penalty or loss of benefit. The subject will not be excluded from any aspect of the main Clinical Study Protocol.

3.1.2 Inclusion criteria

For inclusion in this biologic research, subjects must fulfill all of the inclusion criteria described in the main Clinical Study Protocol.

3.1.3 Exclusion criteria

Exclusion from this biologic research may be for any of the exclusion criteria specified in the main Clinical Study Protocol.

3.1.4 Discontinuation of subjects from this biologic research

Subjects may withdraw from this biologic research at any time, independent of any decision concerning participation in other aspects of the main study. Voluntary discontinuation will not prejudice further treatment. Procedures for discontinuation are outlined in the main Clinical Study Protocol.

3.2 Collection of samples for biologic research

All subjects in participating countries will be asked to participate in this biologic research at Visit 2. If the patient agrees to participate, blood samples will be taken at Visit 2 (Randomization/Baseline) and the remaining visits indicated on the schedule in the main Clinical Study Protocol.

- Blood samples for isolation of serum and plasma will be obtained as follows:
 - Visit 2: Serum (10-mL draw); EDTA-anticoagulated plasma (6-mL draw x 2)
 - Remaining visits: Serum (10-mL draw); EDTA-anticoagulated plasma (6-mL draw)
- Samples will be frozen at -20°C or colder until shipped to the central laboratory on dry ice.

These procedures are detailed in the Laboratory Manual of Operations.

3.3 Coding and storage of samples

The biomarker samples will be labeled (or “coded”) with a study specific code to maintain patient confidentiality. Samples do not carry any patient identifying information. Samples will be stored for up to 20 years after the completion of the study (defined as submission of the clinical study report [CSR] to the appropriate regulatory agencies). At the end of the storage period,

samples will be destroyed. Samples may be stored longer if a Health Authority (or medicinal product approval agency) has active questions about the study. In this special circumstance, the samples will be stored until the questions have been adequately addressed.

3.4 Analytic Plan

3.4.1 Biomarkers of interest

Analysis will be performed of biomarkers of adiposity and metabolic dysregulation, dysglycemia and its complications, and CV risk (atherosclerosis, ischemia, inflammation, thrombosis, and hemodynamic stress) to address the specific 4 aims listed above. A detailed analytic plan will be developed. Candidate biomarkers are listed below, from which a subset will be measured based on the scientific evidence at the time of testing.

Biomarkers of Adiposity/Obesity and Metabolic Dysregulation:

- Adipokines (eg, adiponectin, leptin, resistin, angiotensinogen, IL-6, TNF- α)
- Mediators of appetite (eg, Orexin A, neuropeptide Y, α -melanocyte stimulating hormone, agouti-related protein)
- Biomarkers of Lipid Dysregulation/Insulin Resistance (eg, Lipoproteins and modified/oxidized lipoproteins, Lp(a))

Dysglycemia and its complications

- Glycation end products and associated receptors (eg, AGE, RAGE)

Biomarkers of Cardiovascular Risk

Biomarkers of Oxidative Stress:

- Myeloperoxidase
- ADMA and other arginine metabolism products

Biomarkers of Endothelial Function:

- VCAM-1, ICAM-1, vWF, E-selectin

Biomarkers of Ischemia/Injury:

- Cardiac troponin, FABP

Biomarkers of Inflammation and Atherothrombosis:

- hs-CRP
- Fibrinogen
- phospholipases (eg, Lp-PLA2 and sPLA2)
- metalloproteinases (eg, PAPP-A, MMP-9, MMP-11)
- cytokines (eg, IL-1 β , IL-1Ra, IL-6, IL-18, GDF-15, PIGF)
- chemotactic molecules (eg, MCP-1)
- sCD40L

Biomarker of Renal Dysfunction:

- Cystatin-C, FGF-23, NGAL

Biomarkers of Hemodynamic Stress:

- Natriuretic peptides (eg, BNP, ANP and their NT-prohormones)
- MR-adrenomedullin, C-terminal proendothelin 1, copeptin
- ST-2
- Galectin-3

Specific biomarkers to be tested will depend on the totality of published data at the time analyses are ready to commence. Other markers of these processes may be added or substituted as new evidence comes to light. In addition to analysis of existing biomarkers, proteomics and metabolomic analyses may be performed on samples to develop and test novel protein markers of cardiovascular outcomes. The biomarker samples may be used for discovery and/or validation to identify biomarkers that, for evaluation of response and/or safety-related outcomes as well as for use in diagnostic development.

Sample processing and analysis will be performed by laboratories under the direction of the Sponsor and/or designee. Processing, analysis, and storage will be performed at secure laboratory facilities to protect the validity of the data and maintain subject privacy. Samples will only be used for the purposes described in this protocol.

3.4.2 Biomarker Testing

Biomarkers will be measured in all subjects at baseline with serial testing at three additional timepoints. Testing at serial timepoints may be expanded.

4 ETHICAL AND REGULATORY REQUIREMENTS

The principles for ethical and regulatory requirements for the study, including this biologics research component, are outlined in Section 5 of the main Clinical Study Protocol.

Informed consent

The biologic component of this study is optional and the patient may participate in other components of the main study without participating in the biologic component. The principal investigator(s) is responsible for ensuring that consent is given freely and that the patient understands that they may freely discontinue from the biologic aspect of the study at any time.

Right to Withdraw

If, during the time the samples are stored, a participant would like to withdraw his/her consent for participation in this research, Eisai or its agents will destroy the samples. Information from any assays that have already been completed at the time of withdrawal of consent will continue to be used as necessary to protect the integrity of the research project.

Subject Privacy and Return of Data

No subject-identifying information (eg, initials, date of birth, government identifying number) will be associated with the sample. All biomarker samples will be coded.

The Sponsor will take steps to ensure that data are protected accordingly and confidentiality is maintained as far as possible. Data from subjects enrolled in this study may be analyzed worldwide, regardless of location of collection.

The Sponsor and its representatives and agents may share coded data with persons and organizations involved in the conduct or oversight of this research. These include:

- Clinical research organizations retained by the Sponsor;
- Independent ethics committees or institutional review boards that have responsibility for this research study;
- National regulatory authorities or equivalent government agencies

At the end of the analysis, results may be presented in a final report which can include part or all of the coded data, in listing or summary format. Other publication (eg, in peer-reviewed scientific journals) or public presentation of the study results will only include summaries of the population in the study, and no identified individual results will be disclosed.

Given the research nature of the biomarker analysis, it will not be possible to return individual data to subjects. The results that may be generated are not currently anticipated to have clinical relevance to the patients or their family members. Therefore, these results will not be disclosed to the subjects or their physicians.

5 DATA MANAGEMENT

Biomarker data from the designated laboratory will be merged with the clinical database for statistical analysis.

The results from this biologic research may be reported in the CSR for the main study, or in a separate report as appropriate.

Some or all of the clinical datasets from the main study may be merged with the biologic data in a suitable secure environment separate from the clinical database.

6 STATISTICAL ANALYSIS PLAN

The biomarker analyses are exploratory in nature. A sample size of approximately 10,000 subjects (assuming 80%-90% participation) will provide 80% power to detect a relative risk of ≥ 1.2 for the primary endpoint of MACE and secondary endpoint of MACE+ for subjects above versus those below the median level of a biomarker. These values are in keeping with risk estimates and interactions seen with other biomarkers and represent the thresholds of clinical importance.

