All subjects will continue in the study until study completion rather than for a prespecified number of visits. Subjects will remain in the study even after their first nonfatal MACE event. Subjects who discontinue treatment prematurely will be followed up for safety until study completion (ie, they will attend the remaining study visits for safety assessments).

- In order to reduce intra- and inter-site variability, the CEC will centrally review each potential MACE and MACE+ event to ensure standardization of data collection and interpretation of such events reported throughout the study. The CEC will determine whether each potential event meets criteria for MACE or MACE+. The CEC will remain blinded to treatment allocation and its activities and the criteria for classification of MACE/MACE+ events will be documented in the CEC Charter.

When 460 adjudicated MACE events have occurred, an interim analysis will be conducted on MACE events. It will be conducted to establish whether the primary safety objective (MACE noninferiority) has been achieved. This analysis will be performed by an independent statistician and governed by an independent Data Monitoring Committee (DMC) and is anticipated to occur on or before (approximately) July 2017. (revised per Amendment 02) If the primary safety objective has been achieved, the trial will continue for evaluation of additional endpoints as delineated in the objectives.

As required by some regulatory agencies, the following estimates are provided:

- The study will begin in December 2013.
- 460 MACE events are expected to occur on or before December 2017; the interim analysis is anticipated to occur on or before (approximately) July 2017. (revised per Amendment 02).
- The study will terminate when 1401 MACE+ events have occurred and when there has been a median treatment duration of 2.5 years have accrued. (revised per Amendment 02) This is expected to occur on or before October 2018
- The estimated period for each subject on study is anticipated to be approximately 60 months.

Number of Subjects

Approximately 18,000 subjects will be screened to provide 12,000 randomized subjects.

Inclusion Criteria

1. Body mass index (BMI) $\geq 27 \text{kg/m}^2$
2. Subjects able and willing to comply with a reduced-calorie diet and an increased physical activity program
3. Age ≥ 40 years with established CV disease as defined by 1 of the following:

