The incidence of AEs of interest will be summarized separately. In addition, for each AE of interest, Kaplan-Meier curves and median time and 95%CI will be presented. The Safety Analysis Set will be used for this analysis.

Other Analyses

- Not applicable

Interim Analysis

There will be 1 interim analysis; when 460 adjudicated MACE events have occurred, the primary analysis for MACE will be conducted. This will be the analysis to rule out a hazard ratio of 1.4. The study will continue to accrue events until the required number of MACE+ have occurred. (revised per Amendment 02) Sensitivity analysis for MACE endpoint will be performed after all the MACE+ events have accrued. (revised per Amendment 02) At the time of MACE+ analyses, there will be approximately 600 MACE events.

The interim analysis for MACE endpoint will be performed by an independent statistician and governed by an independent DMC and is anticipated to occur on or before (approximately) Jul 2017. (revised per Amendment 02) The interim analysis will be conducted to establish whether the MACE primary objective has been achieved. To maintain the integrity and credibility of the trial, procedures will be implemented to ensure the DMC and independent statistician have sole access to evolving information from the clinical trial regarding comparative efficacy and safety data aggregated by treatment group. Full details of the DMC procedures including primary responsibilities of the DMC, its relationship with other trial components, its membership, and the purpose and timing of its meetings will be documented in the DMC Charter. These details will also include procedures to ensure confidentiality and proper communication (as outlined in the Study Integrity Charter), the safety and statistical monitoring guidelines to be implemented by the DMC, and an outline of the content of the closed reports and open reports that will be provided to the DMC. (revised per Amendment 02)

At the interim analysis for MACE, the estimate of the hazard ratio of lorcaserin HCl to placebo and the corresponding 97.5% CI will be calculated. Noninferiority between lorcaserin HCl and placebo will be declared if the upper limit of the 97.5% CI is less than or equal to the noninferiority margin of 1.4. If the upper limit of the 97.5% CI is greater than 1.4, then lorcaserin HCl will be declared as not noninferior to placebo and the trial will stop.

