All subjects will continue in the study until study completion, rather than for a prespecified number of visits. Subjects who prematurely discontinue study drug will continue in the study for all subsequent study visits until study completion and are to complete visit procedures as indicated in [Table 4](#). It is preferred that these visits are in person. However, if the subject is unable to attend a visit in person, a telephone visit may be performed. The outcome of the telephone visit must be clearly documented in the source record. At a minimum, the site should attempt to have the subject return for an in-person visit at least once per year. The study will terminate when 1401 MACE+ events have occurred and when there has been a median treatment duration of 2.5 years have accrued. (revised per Amendment 02) This is expected to occur on or before October 2018.

When 460 adjudicated MACE events have occurred, an interim analysis will be conducted on MACE events (see [Section 9.7.3](#)). It will be conducted to establish whether the primary safety objective (MACE noninferiority) has been achieved. This analysis will be performed by an independent statistician and governed by an independent Data Monitoring Committee (DMC) and is anticipated to occur on or before (approximately) July 2017. (revised per Amendment 02). If the primary safety objective has been achieved, the trial will continue for evaluation of additional endpoints as delineated in the objectives.

An overview of the study design is presented in [Figure 1](#).

[figure not shown]

Figure 1 Study Design Schematic

BID = twice daily; EOS = end of study; EOT = end of treatment; R = randomization.

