9.7.1.6 Primary Safety and Key Secondary Efficacy Analyses (revised per Amendment 02)

The primary endpoints, MACE, and MACE+, will be analyzed using a Cox proportional hazards model that includes factors for treatment and stratification variable (presence of established CV disease or CV risk factors without established CV disease). (revised per Amendment 02) For secondary and exploratory endpoints a 2-sided $\alpha = 0.05$ significance level will be used. The MACE analysis (“interim” analysis) will be conducted when 460 adjudicated MACE events have been recorded; the other analyses will be conducted when 1401 adjudicated MACE+ events have been recorded, and the study has completed. (revised per Amendment 02)

Sequential Gatekeeping Testing Procedure (revised per Amendment 02)

The following closed sequential gatekeeping testing procedure (SGTP) will be used to control the family-wise error rate (FWER) at $\alpha = 0.05$ (2-sided) in testing the 2 primary endpoints (MACE and MACE+) and 1 key secondary endpoint, conversion to T2DM. (revised per Amendment 02)

Let H_{01} be the gatekeeping null hypothesis for noninferiority testing of the MACE endpoint using a noninferiority margin of 1.4.

Let H_{02} , and H_{03} be the null hypotheses for superiority testing: MACE+ and conversion to T2DM, respectively. (revised per Amendment 02)

The SGTP testing hierarchy is presented below. (revised per Amendment 02)

- STEP1: At the interim analysis, test the noninferiority hypothesis for MACE, H_{01} ($\alpha = 0.025$, 1-sided). If H_{01} is rejected, then proceed to STEP2, otherwise stop testing and the trial will be stopped.
- STEP2: At study completion, the hypotheses H_{02} ($\alpha = 0.05$, 2-sided), is tested first. If the hypothesis is rejected, then proceed to test H_{03} ($\alpha = 0.05$, 2-sided). If H_{02} is not rejected, then testing stops at this point.

[Figure 3](#) presents the SGTP. (revised per Amendment 02)

Flowchart for the Sequential Gatekeeping Testing Procedure

[figure not shown]

Figure 3 Flowchart for SGTP

MACE = major adverse cardiovascular events, MACE+ = MACE or hospitalization for unstable angina or heart failure, or any coronary revascularization; SGTP = sequential gatekeeping testing procedure; T2DM = type 2 diabetes mellitus.

PRIMARY ENDPOINT ANALYSES

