9.7.2 Determination of Sample Size

A sample size of 12,000 subjects should provide the required power for the primary endpoints as follows: (revised per Amendment 02)

- For 460 MACE events to have occurred by approximately 43 months from start of the trial, providing 95% power to exclude a noninferiority margin of 1.4, assuming an annual background rate of 1.5%, 15-month accrual period, 5% annual drop-out rate, $\alpha = 0.025$, and a 1-sided test
- For 1401 MACE+ events to have occurred by approximately 54 months from the start of the trial, providing >85% power to detect a 15% risk reduction with lorcaserin HCl, assuming an annual background rate of 3.5%, 15-month accrual period, 5% annual drop-out rate, $\alpha = 0.05$, and a 2-sided test (revised per Amendment 02)

Key Secondary Endpoint (revised per Amendment 02)

- For 457 events of conversion to T2DM in subjects who are prediabetic at the time of enrollment (~33%) to have occurred by approximately 54 months from the start of the study, providing 86% power to detect a 25% risk reduction with lorcaserin HCl, assuming an annual background rate of 4%, 15-month accrual period, 5% annual dropout rate, $\alpha = 0.05$ and a 2-sided test. (revised per Amendment 02)

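### Appendix 5 claims 80% power for RR 1.2 on MACE in a biomarker median split; the protocol's own event projection gives about 53% at 2-sided 0.05

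*Protocol*

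**What the plan says.** Appendix 5, section 6 opens with "The biomarker analyses are exploratory in nature". It then states that about 10,000 subjects, at 80-90% participation, "will provide 80% power to detect a relative risk of" 1.2 or more "for the primary endpoint of MACE and secondary endpoint of MACE+ for subjects above versus those below the median level of a biomarker". It calls effects of this size thresholds of clinical importance. It gives no alpha, no sidedness and no event count.

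The body of the protocol supplies what the appendix leaves out:

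- **MACE events.** Synopsis, Interim Analysis (repeated in section 9.7.3): "At the time of MACE+ analyses, there will be approximately 600 MACE events".
- **MACE+ events.** Section 9.1: "The study will terminate when 1401 MACE+ events have occurred", together with a median treatment duration of 2.5 years.
- **Significance level.** Section 9.7.1.6: "For secondary and exploratory endpoints a 2-sided" level of 0.05 applies.
- **MACE planning inputs.** Section 9.7.2: 12,000 subjects, "assuming an annual background rate of 1.5%, 15-month accrual period, 5% annual drop-out rate".

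**The concern.** The sentence attaches one power figure to two endpoints whose projected event counts differ more than twofold (about 600 against 1,401). In a 1:1 comparison of event rates, power is driven by the number of events, so one figure is unlikely to fit both.

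Appendix 5, section 5 allows the biomarker results to be reported in the clinical study report. A reader told that the design had 80% power for RR 1.2 could take a null MACE result for a marker as fair evidence against an effect of that size. At about 53% power, a true RR of 1.2 would be missed nearly half the time.

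**Working it through.** **Inputs.** RR 1.2 (ln 1.2 = 0.1823), a 50:50 split and about 10,000 subjects, from Appendix 5, section 6. About 600 MACE events in 12,000 subjects, from section 9.7.3. 1,401 MACE+ events, from section 9.1. Alpha 0.05, 2-sided, from section 9.7.1.6. Participants are assumed to have the trial-wide event rate.

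**Events that the stated 80% requires.** For a 1:1 split, E = [2(z_α + z_β)/ln RR]².

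- 2-sided 0.05: [2(1.960 + 0.8416)/0.1823]² = 944.5, about 945. Freedman's formula gives 950.
- 1-sided 0.05: [2(1.645 + 0.8416)/0.1823]² = 744.

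**Can the 80% be reproduced?** One route was found. Take 10,000 × 1.5% per year × 5 years = 750 events and test at 1-sided 0.05. Power is Φ(√750/2 × 0.1823 − 1.645) = 80.3%. The same 750 events at 2-sided 0.05 give 70.4%.

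**Is the projection of 600 sound?** Section 9.7.2's rates, with uniform accrual over 15 months and analysis at 54 months, give 12,000 × (0.015/0.065) × the average of [1 − exp(−0.065 f)] for follow-up f between 3.25 and 4.5 years. That average is 0.2225, so about 616 events. The projection agrees with the protocol's own inputs.

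**Power at the projected counts.** Power = Φ(√E/2 × 0.1823 − 1.960).

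| Endpoint and case | Events E | Power, 2-sided 0.05 |
|---|---|---|
| MACE, 10,000 subjects | 600 × 10/12 = 500 | 53.1% |
| MACE, 80% participation | 600 × 0.8 = 480 | 51.5% |
| MACE, 90% participation | 600 × 0.9 = 540 | 56.3% |
| MACE, all 12,000 subjects | 600 | 60.8% |
| MACE+, 10,000 subjects | 1401 × 10/12 = 1,167.5 | 87.6% |
| MACE+, 80% participation | 1401 × 0.8 = 1,121 | 86.3% |
| MACE+, 90% participation | 1401 × 0.9 = 1,261 | 89.9% |

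**Other methods.** At 500 MACE events, Freedman's formula gives 52.9%. A two-proportion test (5,000 against 5,000, 4.55% against 5.45%) gives 55.0%. A simulation of Poisson counts with 200,000 runs gives 53.0%. At 1-sided 0.05 the projected counts still fall short: 65.3% at 500 events and 72.2% at 600.

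**Detectable effect.** RR = exp(2 × 2.8016/√E) is 1.291 at 480 events, 1.285 at 500 and 1.273 at 540.

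**Longer follow-up.** The Synopsis also says "The estimated period for each subject on study is anticipated to be approximately 60 months". If all 12,000 subjects were followed for 60 months at 1.5% per year with 5% annual drop-out, events would be 12,000 × (0.015/0.065) × (1 − exp(−0.325)) = 768, and power 71.4%.

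**The case against.** Four points can be made for the plan.

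1. **The 80% has a possible origin.** The 750-event, 1-sided route reproduces it, and the Aim 2 hypothesis (Appendix 5, section 2) is directional. The fault may therefore be optimistic, unstated assumptions and not a slip of calculation. That may well be so, but the route conflicts with the 2-sided level in section 9.7.1.6, the drop-out and staggered accrual in section 9.7.2, and the projection of about 600 events in section 9.7.3.

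2. **The alpha is borrowed.** Section 9.7.1.6 concerns treatment comparisons, and the biomarker analysis has its own plan (possible under protocol 9.7.1.9, definite under SAP 5.5.3). This stands as a limit on the point value: 53% is conditional on 2-sided 0.05. It does not rescue the claim, because 1-sided 0.05 at the projected counts also stays below 80%.

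3. **Drop-out may be overstated.** Subjects are followed after stopping study drug (sections 9.1 and 9.5.5.1), and section 9.5.5.2 expects full withdrawal of consent to be very rare. With no drop-out, 12,000 subjects followed for 60 months at 1.5% per year give 12,000 × (1 − exp(−0.075)) = 867 events, or 12,000 × 0.075 = 900 on a linear count. Power at 2-sided 0.05 is then 76.6-78.1%. So 71% is not a ceiling. This most favourable case still falls short of 80%, although it uses all 12,000 subjects and well over the projected 600 events.

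4. **Nothing depends on it.** The analysis is exploratory, and the 10,000 is a participation estimate, not a recruitment target derived from this power. This stands and keeps the point minor. It does not make the stated figure correct, and a later biomarker plan would not correct the protocol's sentence.

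**Conclusion.** The concern holds for MACE only. The stated 80% should read about 53%, because about 500 events are expected where about 945 are needed. Across the participation range and the all-subjects case, the shortfall is 19 to 29 percentage points (80 − 60.8 to 80 − 51.5). The exact figure rests on three assumptions: 2-sided alpha of 0.05, events pro-rated from the projected 600, and trial-wide event rates among participants. The existence of a shortfall at 2-sided 0.05 depends on none of the follow-up variants examined. The MACE+ part of the sentence is right and conservative. The primary and key secondary inferences are unaffected.

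**What to change.** Reword the power sentence in Appendix 5, section 6 to give each endpoint its own figure. For a median split at 2-sided 0.05 in 10,000 subjects, state about 53% power for RR 1.2 on MACE (about 500 events; 80% power for RR of about 1.27-1.29) and about 88% for RR 1.2 on MACE+ (about 1,167 events). State the alpha and the assumed event counts, so that a later biomarker plan can update the figures if it chooses another level or model.

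As an editorial alignment only, the same edit can call MACE+ a primary endpoint, as section 9.7.1.1 does; Appendix 5 is a 2013 edition and still calls it secondary.

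The cost is one exploratory sentence and a less favourable stated power for MACE. No extra patients, visits or samples are needed, and the 12,000-subject sample size and the 1,401-event target stay as they are.
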